## **STUDY PROTOCOL**

### **Study Design**

- Crossover design
- Double-blind
- Randomized
- Primary endpoint classification: Change in fat consumption from baseline
- Secondary endpoint classification: Change in energy expenditure from baseline

### **Pre-enrollment Screening**

In this visit the study coordinator, or designated Research Assistant, will review the study's purpose and procedures with prospective participants, answer any questions, obtain written consent from the participant and confirm that the participant meets study inclusion/exclusion criteria by asking them to complete a questionnaire about their medical history and medications to ensure that they fulfil the inclusion and exclusion criteria for the study. The completed questionnaires will be identified using an alphanumeric code and will not have any identifiable subject data on them. The questionnaires will be securely stored in a locked cabinet.

### **First Study Visit**

The first study visit for subjects who pass the screening process will require a visit to the EPARC laboratory for approximately two hours. Subjects should attend fasted from 7.30PM the previous evening, though they are allowed to continue drinking water. Subjects should not have engaged in any significant exercise for 24 hours prior to the test.

Testing will begin between 7AM and 8AM at the EPARC laboratory in the Qualcomm Institute (i.e Atkinson Hall) on the UCSD campus. A free designated parking space will be provided and laboratory staff will escort the subject into the lab where the testing takes place. Participants will have their age, height, weight and gender recorded, and undergo a 15-minute assessment of (sitting) resting energy expenditure (EE) using indirect calorimetry (COSMED, Italy) following a standardized protocol in which the subject is asked to sit quietly while watching a nature or science documentary from Netflix on a (provided) tablet computer. The subject will be fitted

with a mask that captures (and analyzes) all of their expired air to calculate oxygen uptake (VO2), carbon dioxide production (VCO2), energy expenditure (EE), and substrate (carbohydrate and fat) utilization.

The subject will then be randomized to treatment sequences via a randomized block procedure, with block sizes randomly chosen in the set {2, 4, 6}. Subjects will be assigned 1:1 between an initial active stimulation, and initial sham stimulation as a control. This will be done in a double-blind manner, and whichever group a subject is randomized to on their first visit they will crossover to the other group on their second study appointment. So if a subject is initially randomized to what happens to be the active stimulation protocol, then on their second study visit that subject will crossover and receive the sham protocol, and vice versa.

The subject will then undergo 45 minutes of either vestibular nerve stimulation or sham stimulation, as described below. The subject will continue to sit quietly watching a science or nature documentary. During this 45-minute stimulation period the subject will have their EE measured during the middle 15 minutes.

After the 45-minute stimulation period ends the subject will remain in the EPARC facility for one more hour. They will continue to sit quietly and watch a documentary. During this 1-hour post-stimulation period the subject will undergo two more 15-minute measurements of their EE. The first 15-minute measurement will take place during the first 15 minutes of this one-hour post-stimulation period, and the second 15-minute measurement will take place during the final 15 minutes of the one-hour post-stimulation period.

## **Second Study Visit**

The second study visit will take place at least two weeks after the first to allow a suitable washout period from the first study visit. Subjects should attend fasted from 7.30PM the previous evening, though they are allowed to continue drinking water. Subjects should not have engaged in any significant exercise for 24 hours prior to the test.

Testing will begin between 7AM and 8AM at the EPARC laboratory in the Qualcomm Institute (i.e. Atkinson Hall) on the UCSD campus. Again a free, designated parking space will be provided and subjects will be met at their car and escorted into the lab. The total visit will last about two hours. Participants will once again have their age, height and weight recorded, and undergo a 15-minute assessment of (sitting) resting energy expenditure (EE) using indirect calorimetry (COSMED, Italy) following a standardized protocol in which the subject is asked to sit quietly while watching a nature or science documentary from Netflix on a (provided) tablet computer. The subject will be fitted with a mask that captures (and analyzes) all of their expired air to calculate oxygen uptake (VO2), EE, and substrate (carbohydrate and fat) utilization.

The subject will then crossover to receive 45 minutes of either active stimulation or sham stimulation, as described below. As stated above, whichever stimulation arm the subject was randomized to during their first study visit, they will now receive the opposite. The subject will continue to sit quietly watching a science or nature documentary throughout. During this 45-minute stimulation period the subject will have their EE measured during the middle 15 minutes.

After the 45-minute stimulation period ends the subject will remain in the EPARC facility for one more hour. They will continue to sit quietly and watch a documentary. During this 1-hour post-stimulation period the subject will undergo two more 15-minute measurements of their EE. The first 15-minute measurement will take place during the first 15 minutes of this one-hour post-stimulation period, and the second 15-minute measurement will take place during the final 15 minutes of the one-hour post-stimulation period.

### **Stimulation Protocol for Both Active and Sham Devices**

Subjects will have the skin behind their ears cleaned with a disposable alcohol wipe before applying the device. The electrodes that will be used are 25mm in diameter hydrogel electrodes, which are hypo-allergenic. The devices will physically appear identical on the outside and both examiners and subjects will be blinded as to whether the device is active or "sham" control.

The devices will be brought in charged and no charging will take place during their usage in the study. Prior to the session subjects will be counseled that they may or may not experience a

rocking sensation during the stimulation and that not everyone can perceive the vestibular stimulation. This is true and also necessary to prevent subjects distinguishing between the active and sham devices.

There are buttons on the outside of the devices that allow their outputs to be tuned up or down. When initially powered up the devices do not deliver any current. The active device increases its output to the subject in 0.1mA increments. The sham device will discharge its current into an internal resistor rather than the subject.

The devices will be operated by the member of the research team, and over the course of minute or so they will turn it up to a level that the subjects say they are comfortable with for the 45-minute stimulation period. Afterwards subjects will have a little aloe vera gel applied to where the electrodes were, as this is thought to be particularly effective in preventing any skin irritation by VeNS.

### **Specific Measure**

The Cosmed CPET, or portable K4B2, metabolic assessment unit will be used for all measurements of indirect calorimetry. Subjects are fitted with a pliable facemask that covers their nose and mouth, and allows for normal breathing. However, the facemask allows us to measure all of the air the subject inspires as well as the fractional composition of inspired and expired gases. EE and substrate utilization are derived from the VO2 and VCO2 measurements.

The primary endpoint of the study will be change in fat consumption from the baseline measurement, and the secondary endpoint will be the change in energy expenditure from the baseline.

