## 1.2 Analysis Plan and Sample Size Calculation

To account for potential period effects, a cross-over design will be used to assess the effect of VeNS on fat consumption. Subjects will be randomized to either the Sham VeNS sequence or VeNS Sham-sequence. To eliminate the effect of period and sequence effects, standard cross-over design analysis will be performed with an independent samples t-test of differences between the first and second measurement by sequence (Sham → VeNS or VeNS → Sham).

When  $n = 10$  subjects data have been collected, we will perform an interim analysis of the primary aim. Our only considerations will be whether to stop the study to reject the null hypothesis or to continue to full recruitment. As such, we will apply the Pocock alpha spending function to account for the effect of this interim look on the type I error of the study. This amounts to using a significance level of 0.0294 at both the interim analysis and the final analysis, in order to maintain an overall type I error rate of 0.05.

With a total sample size of  $n = 20$  subjects, we will have 80% power at the  $\alpha = 0.05$  significance level (adjusted for two analyses with the Pocock alpha spending function) to detect a medium effect size of  $d = 0.72$ . Assuming a moderate within-subject correlation of  $\rho = 0.50$  and a standard deviation of mean fat consumption over the 60 minute treatment period of  $\sigma = 5.44$ , this translates to a detectable difference in fat consumption of 3.9%.

[figure not shown]

Figure 1: Detectable effect sizes by total sample size (A), and detectable effect sizes in terms of fat consumption assuming certain within-subject correlations (B).

[figure not shown]

Figure 2: Pilot data of energy expenditure over a two hour period for  $n = 3$  subjects.

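### Does naming two possible calorimeters, without tying each subject to one of them, weaken the active–sham comparison?

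*Combined protocol and SAP*

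**What the plan says.** The Specific Measure section of the protocol names the equipment: "The Cosmed CPET, or portable K4B2, metabolic assessment unit will be used for all measurements of indirect calorimetry". The First and Second Study Visit sections give only the manufacturer; the second, for example, has resting energy expenditure measured "using indirect calorimetry (COSMED, Italy) following a standardized protocol". No section assigns a subject to a unit or asks for the unit to be recorded.

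The endpoint is stated twice. Study Design has "Primary endpoint classification: Change in fat consumption from baseline", and Specific Measure has "The primary endpoint of the study will be change in fat consumption from the baseline measurement". Each visit has four 15-minute measurements: a resting baseline before stimulation, one in the middle of the 45-minute stimulation, and two in the hour afterwards. Each visit therefore supplies its own baseline.

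SAP section 1.2 plans "an independent samples t-test of differences between the first and second measurement by sequence". Its sample size calculation uses "a standard deviation of mean fat consumption over the 60 minute treatment period" of 5.44, a within-subject correlation of 0.50, d = 0.72, 20 subjects and a significance level of 0.0294 at each of two looks.

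**The concern.** Fat consumption and energy expenditure are both calculated from the unit's gas measurements, so a difference between instruments feeds directly into both endpoints. The two models named are different machines, one of them portable. If a subject were measured on one under active stimulation and on the other under sham, the difference between machines would be added to the treatment contrast for that subject. If this happened in some subjects and not in others, the variance of the within-subject difference would rise. With 20 subjects and a planned power of 80%, there is little room for extra variance.

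The SAP adds to the doubt. Its test refers to a first and a second measurement, and its standard deviation belongs to a mean over the treatment period; neither mentions baseline. If raw visit values were compared, an offset between units would not cancel.

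**Working it through.** **Inputs.** From SAP section 1.2: SD 5.44, correlation 0.50, d = 0.72, alpha 0.0294 per look, n = 20. From First Study Visit: 1:1 allocation, so 10 per sequence. Two-sided testing and no dropout are assumed. The documents give no between-unit difference and no switching rate, so every such figure below is an assumption. Differences between units are expressed on the fat-consumption scale.

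**The plan's own figure.** SD of the within-subject difference = 5.44 × √(2 × (1 − 0.50)) = 5.44. Detectable difference = 0.72 × 5.44 = 3.92, stated as 3.9%. For the t-test by sequence, the noncentrality is 0.72 × √20 = 3.22 on 18 degrees of freedom. At alpha 0.0294 this gives 79.6% power at the final look, against the stated 80%. Counting the interim look as well, simulated power is 81.3%.

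**Constant offset, one unit per visit.** Suppose one unit reads b higher than the other. Change from baseline at that visit is (later + b) − (baseline + b) = later − baseline. The offset disappears, whichever unit is used at whichever visit.

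**Everyone changes unit at visit 2.** Even if an offset survived, each subject's between-visit difference would shift by the same b in both sequences. The test compares the two sequence means, and (mean₁ + b) − (mean₂ + b) = mean₁ − mean₂. The shift is a period effect and drops out.

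**Proportional difference, one unit per visit.** Let the two units read (1 − g/2) and (1 + g/2) times the true change, with the unit picked 50:50 at each visit, and let fat use drift by m SD in both arms. SD 5.44 and correlation 0.50 are applied to the changes, because the SAP gives no SD for change. The variance of the difference is then multiplied by

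1 + (g/2)² × [2 + m² + (m + 0.72)²].

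If each subject stays on one unit, the factor is 1 + (g/2)² × [1 + 0.72²]. For g = 0.20:

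- random unit, m = 0: 1 + 0.01 × (2 + 0.518) = 1.025
- random unit, m = 1: 1 + 0.01 × (2 + 1 + 2.958) = 1.060
- fixed unit, any m: 1 + 0.01 × 1.518 = 1.015

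Simulated final-look power, 400,000 runs per cell:

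| Gain difference g | No drift: random unit | No drift: fixed unit | 1 SD drift: random unit | 1 SD drift: fixed unit |
|---|---|---|---|---|
| 5% | 79.5% | 79.6% | 79.5% | 79.5% |
| 10% | 79.3% | 79.4% | 79.0% | 79.5% |
| 20% | 78.5% | 79.1% | 77.2% | 79.1% |

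Putting the variance factors into the noncentral t gives the same values to within about 0.2 points. Keeping each subject on one unit therefore gains at most about half a point at 5–10%, and about 2 points only in the most extreme cell.

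**Where the larger losses would come from.** An offset of f SD that does not cancel, in a share p of subjects and in random direction, multiplies the variance by 1 + p × f².

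| Offset | Half affected: factor | Half affected: power | 10% affected: factor | 10% affected: power |
|---|---|---|---|---|
| 0.25 SD (1.4) | 1.031 | 78.2% | 1.006 | 79.3% |
| 0.5 SD (2.7) | 1.125 | 74.4% | 1.025 | 78.5% |
| 1.0 SD (5.4) | 1.500 | 60.9% | 1.100 | 75.4% |

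These rows apply only if the unit is changed between baseline and a later measurement of the same visit, or if baseline is not subtracted. The last offset is larger than the 3.9 that the trial is designed to detect.

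**Type I error.** Rejection under the null in the simulated gain and offset cells was 2.88% to 3.00%, against a nominal 2.94%. Sequence is randomized and examiners are blinded, so the choice of unit cannot favour an arm systematically.

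**The case for a change.** The strongest case for the concern is textual and practical. The choice between the two models is never resolved, and no section ties a subject to a unit. Adding such a sentence would cost almost nothing. If the unit is not recorded, a switch could not be identified afterwards, and no sensitivity analysis could deal with it. The SAP's silence on baseline also leaves open an analysis in which offsets survive.

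Part of this stands. The documents contain no such rule, and recording the unit is good laboratory practice. But the sentence is in the singular and covers all measurements, so a single unit is its natural reading. Testing is seated, in one laboratory and within a fixed morning window, and nothing suggests that staff would change calorimeter between measurements of one visit. Which machine serves which subject is an operating detail that a laboratory can settle in its own procedures. The raw-value reading would depart from an endpoint stated twice as change from baseline. It arises from how SAP section 1.2 words the analysed quantity, which is a separate matter from the choice of calorimeter.

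**Conclusion.** There is no flaw here. Followed as written, with change from a same-visit baseline and a test by sequence, the plan already removes a constant difference between units and any change of unit common to all subjects at visit 2. The remaining exposure is a proportional difference. It costs between nothing and about 1 point of final-look power for assumed gain differences up to 20%, and about 2.4 points (79.6% to 77.2%) if a 1 SD drift in both arms is also assumed. There is no bias, no inflation of type I error and no error in the stated 80%.

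The conclusion rests on one unit serving a whole visit and on the primary analysis using change from baseline, as the protocol states. The power figures are illustrative, since they apply the SAP's SD and correlation for mean fat consumption to changes from baseline.

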## INCLUSION AND EXCLUSION CRITERIA

### **Inclusion Criteria**

1. Signed informed consent
2. Body mass index (BMI) > 25 kg/m^2
3. 18-65 years of age inclusive on starting the study.
4. Successfully completed the screening questionnaire.

### **Exclusion Criteria**

1. History of vestibular dysfunction.
2. History of bariatric surgery, fundoplication, gastric resection or major upper-abdominal surgery (acceptable surgeries include cholecystectomy, hysterectomy).
3. History of skin breakdown, eczema or other dermatological condition (e.g. psoriasis) affecting the skin behind the ears, or of the head and neck.
4. History of weight loss device implantation (e.g. VBloc Maestro or Abiliti).
5. Positive response in Physical Activity Readiness Questionnaire.
6. Currently taking medication for asthma or other breathing conditions.
7. Untreated thyroid disorder (stable treatment for 3 months is acceptable).
8. Other endocrinological causes of weight gain (e.g. Cushing's disease, Cushing's syndrome or acromegaly)
9. Previous diagnosis of HIV infection or AIDS (HIV is known to cause a vestibular neuropathy which would prevent VeNS from working).
10. History of cirrhosis, or liver, kidney or heart failure.
11. Chronic pancreatitis.
12. Treatment with prescription weight-loss drug therapy in the year before starting the study.
13. Tobacco or marijuana smoking in the 6 months prior to study.
14. Known genetic cause of obesity (e.g., Prader-Willi Syndrome).
15. Diabetes mellitus (Types 1 & 2).
16. Diagnosis of epilepsy or use of anti-epileptic medication within six months of starting the study (e.g. for the treatment of peripheral neuropathy)

17. Chronic (more than a month of daily use) treatment with opioid analgesic drugs within the last year.
18. Regular use (more than twice a month) of anti-histamine medication.
19. Use of oral or intravenous corticosteroid medication within two years of starting the study.
20. Use of the beta-blockers atenolol, metoprolol or propranolol within 3 months of starting the study.
21. Current use of tricyclic antidepressant medication for whatever reason.
22. Current alterations in treatment regimens of anti-depressant medication for whatever reason (other than tricyclic antidepressants) (Note: stable treatment regimen for prior six months acceptable).
23. An active diagnosis of cancer.
24. A previous myocardial infarction.
25. A history of stroke or severe head injury (as defined by a head injury that required intensive care). (In case this damaged the neurological pathways involved in vestibular stimulation).
26. Presence of permanently implanted battery powered medical device or stimulator (e.g., pacemaker, implanted defibrillator, deep brain stimulator, vagal nerve stimulator etc.).
27. Psychiatric disorders (including untreated severe depression, schizophrenia, substance abuse, bulimia nervosa etc.)
28. Current participant in a clinical trial for weight loss.

## RISK ASSESSMENT

### General Risks

1. Information of a personal nature will be collected in order to determine eligibility for the study, and therefore there is a risk of loss confidentiality.
2. Subjects may experience some degree of distress or anxiety due to confusion, the personal nature of the questions, the VeNS, or their disqualification based on the exclusion criteria.

### Risks related to VeNS

1. Skin irritation at the electrode sites.
2. That the stimulation sites may be uncomfortable at the time of stimulation – an electrical tingling sensation may occur and also VeNS may induce the sensation of being pushed towards the side of the cathode.
3. A sensation of disequilibrium, analogous to being on a boat, may occur during the test that some subjects find uncomfortable.
4. VeNS may induce nausea.
5. VeNS may occasionally induce vomiting.

### Risks related to Indirect Calorimetry

1. Risk of infection from the facemask used during indirect calorimetry.

It is possible some subjects may find the facemask to be claustrophobic.

## **RISK MANAGEMENT**

### Risks Related to Vestibular Nerve Stimulation (VeNS)

1. Any potential subjects a history of irritation to the skin behind the ear will be excluded
2. Hypoallergenic hydrogel electrodes of 25mm diameter will be used in order to minimize the likelihood of skin irritation.
3. Subjects will be asked to apply aloe vera gel to minimize any skin irritation after using the device.
4. Prior to the beginning of the study the possible discomforts of VeNS will be described to the participant in lay language, and the investigator will make sure that the subject understands what will happen when using the device.

5. The usage of the device is limited to 45 minutes and a member of the experimental team will oversee.
6. Usage is voluntary, and subjects will be informed at the beginning of the study that they may withdraw at any time, for any reason, with no negative repercussions.
7. Subjects will be warned about the sensation of disequilibrium which may occur and will only be using the device while seated.
8. The maximum current the device can deliver is 1.0mA but there is no requirement for the subjects to use it at this level. Instead they will be asked to indicate when the experimenter has reached a level that is comfortable. The minimum setting is 0.1mA and the current can be increased in 0.1mA increments.
9. If subjects find the sensation invoked at the level the current is set, to be uncomfortable (e.g. in terms of nausea or disequilibrium) then they can ask for a lower, and more comfortable, stimulation level.
10. The subjects can take off the devices at any point they wish.

#### Risks pertaining to indirect calorimetry

1. The risk of infection is minimized by cleaning the mask using liquid glutaraldehyde disinfectant (e.g. Cidex) which is consistent with CDC recommendations. We use EPA-registered sterilants for this purpose in our laboratory.
2. Subjects can remove the facemask at any time during the experiment if they feel that they no longer wish to continue.

#### **CONFIDENTIALITY**

1. Subject's information will be kept strictly confidential to the extent provided by law. An alphanumeric code will be assigned to each subject, and this code will be used in place of a name when reporting data. The hardcopy corresponding subjects with codes will be kept in a locked data cabinet in Mandler Hall, along with all results of all screening questionnaires. The computer to be used for data collection and analysis will require a password for access,

which only personnel directly involved in the study will have. Data in any format will only be available for those on the protocol. Information collected in the study will not be reused or disclosed for other purposes. Data collected in the study will be destroyed after seven years.

2. All aspects of the study will be explained to the subject in lay language, and the experimenter will make sure that the subject understands what will happen prior to his/her participation. The experimenters will inform the subject of the precautions that will be taken with regard to personal information collected during the course of the study. The study will be as short as possible. Participation is voluntary, and subjects will be informed at the beginning of the study that they may withdraw at any time, for any reason, with no negative repercussions. The research should in no way result in social stigmatization or any other long-term distress to the subjects.
3. In order to minimize the risk of coercing subjects to participate, and in keeping with the UCSD HRPP guidance in this area no attempts to recruit subjects during undergraduate classes will be made.
4. Similarly, due to the risk of coercion the following will be excluded from participating: graduate students in Psychology; undergraduate students working as research assistants at the CBC; and employees in Psychology.

